10.4 Vital Signs

Vital sign measurements of systolic and diastolic blood pressures (sitting and standing), pulse rate (sitting and standing), respiratory rate, temperature, weight, orthostatic systolic blood pressure, orthostatic diastolic blood pressure, and orthostatic pulse rate will be summarized on Safety Populations 1 and 2.

Each vital sign variable will be summarized for all time points (starting with Baseline) with the number of non-missing observations, mean and standard deviation, median, Q1, Q3, minimum and maximum. Mean change from baseline to each applicable post-baseline visit will be summarized for each vital sign variable, with the number of observations, baseline mean, and visit mean. The change from baseline mean, standard deviation, median, Q1, Q3, minimum and maximum will also be presented.

Vital sign variables will be evaluated based on PCS criteria (Table 6). For each vital sign PCS criterion, the number and percentage of subjects who have a vital sign value meeting the criteria will be summarized. Listings will be provided to summarize subject-level vital sign data for subjects meeting PCS criteria.

10.5 Other Safety Analyses

10.5.1 Electrocardiogram

Descriptive statistics for ECG parameters (i.e., heart rate, PR interval, QRS interval, RR interval, QT interval, and QTc interval) at baseline, postbaseline, and changes from baseline values at each postbaseline timepoint will be presented for the Safety Populations 1 and 2.

ECG parameter values are considered PCS if ECG values meet either the actual value or change from baseline PCS high criteria listed in Table 7. The number and percentage of subjects with PCS postbaseline values will be summarized. The percentages will be calculated relative to the number of subjects with an available non-PCS baseline value and at least 1 postbaseline assessment. The numerator will be the total number of subjects with an available non-PCS baseline value and at least 1 PCS postbaseline ECG value during the study. A supportive listing of subjects with PCS postbaseline values will be provided. A listing of all AEs for participants with PCS ECG values will also be provided.

The number and percentage of subjects meeting each of the criteria for postbaseline ECG values of clinical interest listed in Table 5 will be summarized. Subjects will be counted only once for the most severe category. A supportive listing of participants with postbaseline QTcF increases > 30 msec will be provided, including the PID number, study center, and all QTc values (including changes from baseline). A listing of all AEs for participants with postbaseline QTcF increases > 30 msec will also be provided.

A shift table from baseline to the end of open-label treatment period in the investigator's overall interpretation of the ECG will be presented for the following categories: normal; abnormal, not clinically significant; abnormal, clinically significant. A tabular display of subjects with postbaseline clinically significant ECG abnormalities according to the investigator's overall interpretation will be provided.

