10.3 Laboratory Data

Data collected from central laboratories, including additional laboratory testing due to an SAE, will be used in all analyses, except for Baseline where SAE-related laboratory assessments on or before the first dose of study drug without timestamp will be excluded. The details for SAE-related laboratory baseline can be found in the SPP. The clinical laboratory tests defined in the protocol (e.g., hematology, clinical chemistry and urinalysis) will be summarized.

Each laboratory variable will be summarized for all time points (starting with Baseline) with the number of non-missing observations, mean and standard deviation, median, Q1, Q3, minimum and maximum. Mean change from baseline to each applicable post-baseline visit will be summarized with the number of observations, baseline mean, and visit mean. The change from baseline mean, standard deviation, median, Q1, Q3, minimum and maximum will be presented for the mean change from baseline. In addition, descriptive statistics for values and changes from the baseline values in conventional units at each assessment time point will be presented for selected clinical laboratory parameters listed in Appendix D. A description of reporting the lab values in conventional units in patient narratives (along with the standard reporting in SI units) is presented at the end of Appendix D.

Changes in laboratory parameters will be summarized using shift tables categorized as low, normal, or high based on the normal ranges of the laboratory used for each sample. A shift table will be provided to summarize shifts from baseline to the final post-baseline value for all lab categories.

Laboratory abnormalities will be evaluated based on potentially clinically significant (PCS) criteria (Table 4). For each laboratory PCS criterion, the number and percentage of subjects who have a laboratory value meeting the criteria will be summarized in Safety Populations 1 and 2 for each treatment period and overall. Listings will be provided to summarize subject-level laboratory data for subjects meeting PCS criteria.

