The number and percentage of subjects meeting each of the criteria for postbaseline hepatic laboratory abnormalities listed in Table 5 will be summarized. The percentages will be calculated relative to the number of subjects with at least 1 available postbaseline assessment. The numerator will be the total number of subjects having at least 1 postbaseline value that meets the specific category during the study. A supportive listing will also be provided.

The number and percentage of subjects with an adjudicated case (i.e., ALT \geq 3 x ULN and/or AST \geq 3 x ULN) will be summarized by relationship of ALT or AST elevation to study medication. The percentages will be calculated relative to the number of subjects with at least 1 adjudicated case. The numerator will be the number of subjects with at least 1 adjudicated case in the specific category of relationship. If a subject has more than 1 adjudicated case, he or she will be counted in the most relevant category of relationship.

Subjects with an adjudicated case (i.e., ALT \geq 3 x ULN or AST \geq 3 x ULN) will be listed with their ALT and AST assessments, adjudication dates, relationship of ALT or AST elevation to study medication, and confounding factor(s). Additional listings will be provided for subjects who meet ALT \geq 3 x ULN or AST \geq 3 x ULN and/or potential Hy's law and have one of the following categories: at least 1 abnormal liver biochemistry risk factor, at least 1 liver disease sign and symptom, at least 1 liver diagnostic test performed, consultation with a specialist for liver evaluation, liver lab tests performed, and drug screen performed, respectively.

Potential Hy's Law criteria within a 24-hour window is defined by a postbaseline evaluation of alanine aminotransferase (ALT) or aspartate aminotransferase (AST) \geq 3 x ULN, along with total bilirubin (TBL) \geq 2 x ULN and a non-elevated alkaline

phosphatase (ALP) < 2 x ULN, all based on blood draws collected within a 24-hour period. Patients who meet the potential Hy's Law criteria will be summarized. Supportive listing will also be provided.

A listing of urine pregnancy test results will be provided for female subjects of child-bearing potential with at least one positive result.

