SBP = Systolic blood pressure; DBP = Diastolic blood pressure; bpm = beats per minute

ECG parameter values are considered PCS if ECG values meet either the actual value or change from baseline PCS high criteria listed in the following table.

Table 7. Potentially Clinically Significant Criteria for ECG Parameters

Parameter	Unit	Criterion
QRS interval	msec	≥ 150
PR interval	msec	≥ 250
QTc (QTcB or QTcF) interval	msec	> 500
QTc (QTcB or QTcF) interval	msec	Increase from baseline > 60

Table 8. ECG Post-baseline Values of Clinical Interest

Parameter	Unit	Criterion
QTcF interval	msec	> 450
		> 480
		> 500
		Increase > 30 but ≤ 60
		Increase > 60

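### ECG flags (Tables 7 and 8) and part of the hepatic Table 5 have no planned count for the concomitant-use period, so Safety Population 2 tables mix findings from before and after ubrogepant

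*SAP*

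**What the plan says.** Period 1 below is the atogepant-only period and Period 2 the concomitant-use period.

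- **ECG flags, Table 7 (SAP 10.5.1).** The numerator is subjects "with an available non-PCS baseline value and at least 1 PCS postbaseline ECG value during the study". For the denominator, "The percentages will be calculated relative to the number of subjects with an available non-PCS baseline value and at least 1 postbaseline assessment". Neither is tied to a period.
- **ECG values of clinical interest (SAP 10.5.1).** The text says that the "criteria for postbaseline ECG values of clinical interest listed in Table 5 will be summarized" and that "Subjects will be counted only once for the most severe category". No period is named. Table 5 holds hepatic criteria; the ECG criteria are in "Table 8. ECG Post-baseline Values of Clinical Interest" (Appendix C).
- **Hepatic categories, Table 5 (SAP 10.3).** A subject counts with "at least 1 postbaseline value that meets the specific category during the study".
- **Potential Hy's law (SAP 10.3).** "Patients who meet the potential Hy's Law criteria will be summarized", with no period named.

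Three other safety outputs are split. Table 4 laboratory flags "will be summarized in Safety Populations 1 and 2 for each treatment period and overall". SAP 10.2.1 gives treatment-emergent adverse events for each period and for the whole treatment period. SAP 10.5.2 does the same for C-SSRS and adds follow-up.

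**The concern.** The primary objective is the safety of taking ubrogepant on top of atogepant. Ubrogepant enters only in Period 2, so the count that answers the objective is a Period 2 count. For the flags listed above, the written rules give a whole-study count or leave the window open.

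Presenting the table for Safety Population 2 does not settle this. SAP 4.0 defines that population by having been dosed in Period 2, which selects people and not a time window. The Table 4 sentence in SAP 10.3 names population and period separately, so the SAP itself treats them as two different things. A reader of a Safety Population 2 flag table could take a finding first seen on atogepant alone for one seen on the combination, or take the percentage as a concomitant-use rate.

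**Working it through.** **1. The plan's own figures.** SAP 2.4 and Protocol 7.8 start with about 235 subjects and assume that 15% stop in Period 1: 235 × (1 − 0.15) = 199.75, about 200. The stated 95% half-width is about 3% to 5%. No event rate is given, so the rate p is an assumption here. With half-width = 1.96 × √(p(1 − p)/n):

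| n | p = 5% | p = 10% | p = 15% |
|---|---|---|---|
| 235 | 2.8% | 3.8% | 4.6% |
| 200 | 3.0% | 4.2% | 4.95% |

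The stated precision is reproduced for rates of roughly 5% to 15%. The SAP therefore plans for estimates in either period, although it says so for adverse events of interest and not for ECG or laboratory flags.

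**2. What falls before ubrogepant.** From Protocol Appendix D:

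- ECG is scheduled at Visits 1, 5 and 8/Early Termination. With the pre-first-dose baseline, the postbaseline ECGs are Visits 5 and 8.
- Laboratory tests are scheduled at every visit. Postbaseline visits are 3 to 9, which is seven (six without Visit 9).
- Ubrogepant is first dispensed at Visit 5, for use as needed. I assume that Visit 5 assessments come before the first ubrogepant dose.

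So 1 of 2 postbaseline ECGs and 3 of 7 postbaseline laboratory visits (3 of 6 without Visit 9) precede ubrogepant. All can enter a Safety Population 2 count that runs over the whole study.

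**3. Denominator.** The ECG denominator asks for one postbaseline assessment. A subject who enters Period 2 with a Visit 5 ECG and no later one counts as assessed without any ECG on the combination.

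**4. The once-only rule for Table 8.** Without a period, a larger QTcF increase at Visit 5 can take a subject's single entry, so that a smaller increase at Visit 8 is not shown. The SAP does not rank the absolute thresholds against the increases, so I work no numerical case.

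**5. How much of Table 5 is affected.** Table 5 has five parameters with seven grades each, two concurrent rows and one Hy's law row: 5 × 7 + 2 + 1 = 38.

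- Table 4 already gives four of these by period: ALT, AST and ALP at ≥ 3 × ULN, and bilirubin at ≥ 1.5 × ULN. That leaves 38 − 4 = 34.
- Protocol 5.5 lists as withdrawal criteria ALT or AST ≥ 8 × ULN, and ≥ 3 × ULN with bilirubin > 2 × ULN. This bears on the ≥ 10 and ≥ 20 rows for ALT, AST and the two combined (six rows), the concurrent row at bilirubin ≥ 2 × ULN, and Hy's law: eight rows in which a Period 1 case would normally not reach Period 2. That leaves 34 − 8 = 26.

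The 26 include the lower grades, the ≥ 5 × ULN rows (the ≥ 5 × ULN withdrawal criterion requires more than 2 weeks) and the combined ALT-or-AST rows up to ≥ 5 × ULN. The combined ≥ 3 × ULN count cannot be recovered from the separate Table 4 counts; it lies between the larger of the two and their sum.

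**6. What pooling can hide (hypothetical count).** Suppose a Safety Population 2 ECG table shows 4 flagged of 200, all with ECGs at both visits: 2.00%, exact 95% CI 0.55% to 5.04%. The count of subjects flagged in Period 2 could be anything from 0 of 200 (0%, CI 0% to 1.83%) to 4 of 200. The table does not say which.

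**The case against.** The strongest reply is that little is lost in practice.

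- **Findings can be dated.** There are only two postbaseline ECGs. SAP 10.5.1 plans by-timepoint statistics, a listing of subjects with PCS values, and a listing of all QTc values for subjects with QTcF increases above 30 msec. Hepatic listings are also planned. This stands for individual cases. It does not supply a planned proportion or a Period 2 denominator, by-timepoint means do not show outliers, and the ECG shift table covers only the investigator's overall interpretation.
- **Liver is largely covered.** This stands in good part. A reader might infer that no concomitant-period liver count is planned at all; Table 4 shows otherwise. Events of special interest are also reported on the AE form, so they should reach the by-period adverse event tables.
- **Period 1 Hy's law cases would not contaminate Safety Population 2.** A reader might infer that they would. The Protocol 5.5 criteria leave only narrow routes, such as a Visit 5 sample reported after Period 2 dosing, bilirubin of exactly 2 × ULN, or a subject not withdrawn as listed.
- **Early terminations.** Visit 8 and Early Termination share one column in Protocol Appendix D, which might suggest that Period 1 dropouts enter the Period 2 picture. Subjects who stop in Period 1 are outside Safety Population 2 by definition. An allocation rule is still needed for tables by period.
- **The sample-size statement concerns adverse events, not flag tables.** Correct. It shows the intent to estimate by period; it does not promise precision for these flags.
- **No control group.** A split dates findings and cannot attribute them to ubrogepant. The same limit applies to the adverse event tables, which are split anyway.

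**Conclusion.** The point holds within limits. Tables 5 and 7 are counted over the whole study, and Table 8 and potential Hy's law have no stated window, while comparable safety outputs are split by period. The gap is clearest for the Table 7 and Table 8 ECG counts, where half of the scheduled postbaseline ECGs precede ubrogepant. For liver it is confined to Table 5 rows that Table 4 does not give by period, chiefly the lower grades, ≥ 5 × ULN and the combined ALT-or-AST rows. For potential Hy's law and the highest ALT/AST grades the practical effect is small.

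The documents do not support reading this as lost safety data. What is missing is a prespecified concomitant-period count with its own denominator. The conclusion assumes that Visit 5 assessments precede the first ubrogepant dose and that the withdrawal criteria are applied as listed. No flag rate is assumed. The Table 5 pointer in SAP 10.5.1 is a clerical error. Severity: minor to should-fix.

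**What to change.** 1. In SAP 10.3 and 10.5.1, summarize the Table 5, potential Hy's law, Table 7 and Table 8 flags by treatment period and overall, as SAP 10.3 already does for Table 4.
2. Use as denominator the subjects with at least one assessment in that period; for ECG PCS, also require a non-PCS baseline. Apply the Table 8 most-severe rule within each period.
3. Assign Visit 5 values taken before ubrogepant to Period 1 and early-termination values to the period in which the subject stopped. State where Visit 9 values belong. SAP 7.3 already has a period rule for concomitant medications.
4. In SAP 10.5.1, change the reference for ECG values of clinical interest from Table 5 to Table 8.
5. Keep the single pre-first-dose baseline of Protocol 7.5 and SAP 10.1.

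Optionally, state a window for the vital-sign flags in SAP 10.4, which also names none.

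Cost: SAP wording and by-period runs of tables already planned; no new data. The price is a few more tables, and without a control group they show when a finding occurred, not what caused it.

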		
Added ubrogepant take dose subgroup definition in Section 9.4
 
Removed MMRM model-based analysis for under subgroup analysis for Section 9.4.
 
Removed analysis in AESI section as it's covered in Section 10.3.
 
Added subgroup analysis for safety (Section 10.6).
 
Updated Appendix A to clarify MTOQ6's definition.
 
Updated Appendix B, protocol deviation section to align with standard.
 
Removed Appendix C as AESIs are defined in the SAP body.
 
Updated Appendix index accordingly.
 
Updated mITT 1 and mITT 2 population definitions with "received" instead of "receive" in Section 4.0.
 
Added that baseline analyses are done for both Safety Population 1 and Safety Population 2 in Section 4.0.
 
Reorganized the subject categories in Section 5.0. Deleted analyses description that were repeated.
 
Added subject accountability by investigator in Section 5.0.
 
Clarified definition for duration of treatment for both atogepant and ubrogepant and the analysis populations in Section 6.0.
 
Specified demographic groups in Section 7.1. Added "migraine prevention medication in the past" to disease characteristics (migraine history) in Section 7.1.
 
Added definitions for concomitant medication for each period in Section 7.3.
 
Updated in Section 9.2 that efficacy analyses are based on observed case (OC).
 
Clarified the meaning of patient satisfaction responder in Section 9.3.2.
 
In Section 9.4, added details about efficacy subgroup analyses and the analysis populations.
 
Deleted MedDRA version in Section 10.2.1 as it's repeated.
 
Specified that study drug include atogepant and ubrogepant in Section 10.2.2.
 
Added analyses detail for Section 10.2.3 (TEAE by SOC & PT), Section 10.2.4 (SAE & AE leading to study drug discontinuation), and Section 10.3 (laboratory data).
 
Clarified potential Hy's law analysis in Section 10.3
 
For Section 13.0, deleted efficacy evaluation under COVID-19 related analyses, specified the analysis populations, added TEAE leading to study discontinuation related to COVID-19.

Version	Date	Summary
		Moved ECG post-baseline values of clinical interest to appendix Table 8 (newly added). Changed the table numbering accordingly.

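### SAP 10.5.1 counts each subject once against open-ended QTcF thresholds, so the > 450 and > 480 msec rows will print fewer subjects than met them, and the scope of the once-only rule is not stated

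*SAP*

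**What the plan says.** SAP 3.1 makes ECG variables part of the primary (safety) endpoint. SAP 10.5.1 plans a table of subjects "meeting each of the criteria for postbaseline ECG values of clinical interest listed in Table 5 will be summarized". Its next sentence sets the counting rule: "Subjects will be counted only once for the most severe category".

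Table 5 holds hepatic criteria. The ECG criteria are in Appendix C under "Table 8. ECG Post-baseline Values of Clinical Interest", and the version history for SAP 2.0 records that they were moved there. Table 8 has five QTcF rows in two families:

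- absolute values: > 450, > 480 and > 500 msec, none with an upper bound;
- changes from baseline: "Increase > 30 but ≤ 60", and increase > 60.

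For the hepatic table, whose rows are also open-ended thresholds, SAP 10.3 sets a different rule: "The numerator will be the total number of subjects having at least 1 postbaseline value that meets the specific category during the study".

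**The concern.** The two sentences in 10.5.1 ask for different tables. Reporting everyone who meets each criterion puts a subject with QTcF 485 msec in both the > 450 and > 480 rows. Counting that subject once puts them in > 480 only. Since the > 450 row has no upper limit, a reader will take it as the number of subjects above 450 msec, and it will not be.

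The rule is also incomplete. The absolute rows have an obvious severity order, and so do the change rows, but the SAP does not rank one family against the other. It does not say whether a subject with QTcF 455 msec and an increase of 40 msec goes in one row or two. Two programmers could follow 10.5.1 faithfully and produce different tables. In an open-label study that choice should be fixed before the data are seen.

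**Working it through.** The documents state no count for this table, so there is no planned figure to reproduce. The check lists every type of subject the table can meet and asks where each would be counted.

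**Inputs.** Row definitions come from SAP Appendix C, Table 8. The counting rule comes from SAP 10.5.1 and the comparison rule from SAP 10.3.

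**Step 1: subject profiles.** At one assessment, QTcF falls in one of 4 bands (≤ 450, > 450 to 480, > 480 to 500, > 500). The change falls in one of 3 bands (≤ 30, > 30 to 60, > 60). That gives 4 × 3 = 12 profiles.

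**Step 2: profiles that meet each row.**

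- > 450: 3 bands × 3 changes = 9
- > 480: 2 × 3 = 6
- > 500: 1 × 3 = 3
- increase > 30 to 60: 4 × 1 = 4
- increase > 60: 4 × 1 = 4

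**Step 3: profiles counted under each reading of the rule.**

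| Reading | > 450 | > 480 | > 500 | Increase > 30 to 60 | Increase > 60 |
|---|---|---|---|---|---|
| Meets the row (SAP 10.3 rule) | 9 | 6 | 3 | 4 | 4 |
| Once within each family | 3 | 3 | 3 | 4 | 4 |
| Once across all rows, absolute ranked first | 3 | 3 | 3 | 1 | 1 |
| Once across all rows, change ranked first | 1 | 1 | 1 | 4 | 4 |
| Once across all rows, interleaved* | 1 | 2 | 3 | 2 | 3 |

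*Order: > 500, increase > 60, > 480, increase > 30 to 60, > 450.

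These are counts of profiles, not predicted patient numbers.

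**Step 4: what the table shows.**

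- The > 450 and > 480 rows are short under every reading tested (at most 3 of 9, and at most 3 of 6).
- The increase rows are short only if the single count spans both families and at least one absolute row outranks them. Counted within family, they lose nothing at a single assessment.
- If change is ranked first, even > 500 is short (1 of 3).
- Within family, adding rows restores the cumulative figures: 3 + 3 + 3 = 9 and 3 + 3 = 6. With change ranked first or interleaved it does not: 1 + 1 + 1 = 3 and 1 + 2 + 3 = 6, against 9.

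**Step 5: in patients.** Counted within family, if N subjects exceed 450 msec and k of them also exceed 480, the > 450 row prints N − k. With assumed values N = 15 and k = 2 it prints 13. For k from 0 to 6 it prints 15 down to 9. Neither N nor k can be taken from the documents.

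**The case against.** The strongest reply is that the second sentence of 10.5.1 simply sets the counting rule for the first, so there is no contradiction. Worst-category counting is a standard convention used elsewhere in this SAP: highest AE severity (10.2), a single relationship category per adjudicated subject (10.3) and most severe suicidal ideation (10.5.2). The most severe category has an obvious meaning only within a family, and the bounded lower change row fits that reading. Exclusive bands are as valid as cumulative rows. This stands as a defence of the convention. It does not rescue labels without upper bounds, because exclusive counting printed under > 450 is a mislabelled count.

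The second reply is that no information is lost. SAP 10.5.1 states: "A supportive listing of participants with postbaseline QTcF increases > 30 msec will be provided", with all QTc values and changes. Anyone who meets a row in both families has an increase above 30, so they appear there with both figures. Values > 500 and increases > 60 are also summarised under the Table 7 criteria, for subjects whose baseline did not already meet them. SAP 3.3 promises subject-level listings of all safety data. This limits the harm but does not correct the printed counts. A subject at 485 msec with an increase of 20 is in neither the > 30 msec listing nor the Table 7 summary, and would be missing from the > 450 row.

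A reader might go further and infer that all of Table 8 is nested and that the increase rows are certain to be understated. The documents do not support that. The two change rows cannot both apply at one assessment, and their shortfall needs a cross-family count and a ranking that the SAP never states. A subject with > 30 to 60 at one visit and > 60 at another would appear only under > 60, which is the ordinary worst-value convention.

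**Conclusion.** The point holds for the > 450 and > 480 rows. As written, each omits any subject who also exceeded a higher threshold, contrary to the promise to report everyone meeting each criterion and to the rule the SAP uses for its hepatic table. For the absolute rows this assumes only the natural severity order, > 500 over > 480 over > 450.

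The scope of the single count is a separate gap. A subject meeting both an absolute and an increase criterion is dropped from one only if the count runs across families, and the increase rows lose subjects only if an absolute row is ranked above them.

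The documents do not give the size in patients. Percentage understatements could be produced from assumed overlaps, but they would reflect the assumptions rather than the plan. Importance is moderate. This is one descriptive table in a single-arm study, with two scheduled postbaseline ECGs (Visits 5 and 8 in the protocol's activity schedule), and no test or stopping rule depends on it. It does report a component of the primary endpoint, and it is easily put right.

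**What to change.** In SAP 10.5.1 and Table 8:

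1. Change the pointer from Table 5 to Table 8.
2. Choose one treatment of the absolute rows. Either count every subject with at least one postbaseline value meeting each row, as in SAP 10.3, or relabel the rows as > 450 to ≤ 480, > 480 to ≤ 500 and > 500 and keep worst-category counting.
3. Replace the once-only sentence rather than just deleting it, because the change rows still need such a rule across visits. The replacement should say that absolute values and changes from baseline are counted separately, and that within the change rows a subject is counted once, at the largest increase.

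The cost is a few lines of SAP wording and a programming change to one table. No new data are needed.
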